## 1. Study Synopsis

Title/Acronym:
Evaluations of Alcohol Warning Labels
Funding Source(s):
NIH
Investigational Intervention(s) and/or Product(s): Different types of alcohol warning labels
Purpose: To test the effectiveness of alcohol warning labels to communicate the cancer risk of alcohol
Objectives: To examine alcohol consumers' reactions to alcohol warning labels that feature narrative or non-narrative content
Design/Methodology: Randomized experiment
Outcome Measures: Affective and cognitive responses toward alcohol warning labels, beliefs, attitudes, intentions, and behaviors related to alcohol
Study Population: U.S. adult (21+) moderate and heavy drinkers
Study Duration: 1 minute for the screening survey; 15 minutes for the main experiment; 5 minutes for the follow-up survey.
Settings/Locations: Surveys will be conducted online

## 2. Rationale/Significance

Alcohol use is a major preventable risk factor for cancer in the United States, but few Americans are aware of the risk (R. Ma & Ma, 2022). A promising approach to raising awareness of risk is to include pictorial warning labels (PWLS) on alcohol-containing products, but there is a limited understanding of the design and impact of such warnings (Clarke et al., 2021; Z. Ma, 2022). The proposed project is relevant to public health because determining the effectiveness of pictorial warning labels that feature narrative content to communicate cancer risk can raise awareness and potentially reduce harm.

## 3. Purpose and Objectives

### 3.1. Purpose

The proposed project aims to evaluate the impact of narrative (vs. non-narrative) PWLS on visual attention, message reactance, risk perceptions, and intentions to reduce and stop drinking.

### 3.2. Objectives

Specific Aim 1: Determine the effect of narrative PWLS on visual attention and message reactance.

Specific Aim 2: Determine the effect of narrative PWLs on risk perceptions and intentions.

### **3.3. Hypotheses/Research Questions**

H1: We hypothesize that narrative PWLs will lead to greater visual attention and less message reactance than non-narrative PWLs.

H2: We hypothesize that narrative PWLs will lead to higher risk perceptions and higher intentions to reduce and stop drinking than non-narrative PWLs.

## **4. Study Design**

To examine the effect of narrative and non-narrative PWLs on visual attention, reactance, risk perceptions, and behavioral intentions, we will employ an online randomized experiment through the Qualtrics survey platform, which can be configured to redirect participants to Sticky by Tobii, a webcam-based eye-tracking platform. We plan to recruit adult moderate and heavy alcohol users via Prolific, a research company that provides online study panels. Participants will first be invited to participate in an online screening survey. Eligible participants will be invited to participate in the main experiment. In the main experiment, participants will first answer questions concerning baseline alcohol consumption and other background information. Then they will engage with a webcam-based eye-tracking task through Sticky by Tobii. Participants will first read instructions and tips related to completing the eye-tracking task. They will complete a brief calibration procedure and be presented with either three narrative PWLs or three non-narrative PWLs. Sticky by Tobii will record participants' gaze, thereby measuring visual attention to each PWL. After viewing each PWL, participants will answer a few questions. After viewing all three PWLs, they will answer questions based on all images combined. Upon study completion, participants will be compensated. A follow-up survey will be sent to participants after two weeks, which includes questions about their drinking behaviors and risk perceptions.

## **5. Analytical Plan**

We will analyze the data using the statistical software SPSS. First, we will use descriptive statistics to provide study sample characteristics. Then, we will conduct independent-samples *t*-tests and chi-square tests to check whether there are differences in background variables (i.e., demographic characteristics and baseline alcohol consumption) between conditions. If there are a significant association between the experimental condition and a specific background variable(s), we will control for this variable(s) in all analyses. To test the first hypothesis, we will conduct multilevel mixed-effects linear regressions to examine the effect of narrative (vs. non-narrative) PWLs time until noticed, time viewed, and number of visits, and reactance. We will also control for repeated measures because each participant will view three PWLs that vary in cancer type within their assigned

condition. We will check the assumptions of these analyses. To test the second hypothesis, we will conduct independent-samples t-tests to examine the effect of PWLs type (narrative vs. non-narrative) on risk perceptions and behavioral intentions when there are no differences in the distribution of background variables between conditions. If there are differences in the distribution, we will conduct a series of analyses of covariance (ANCOVA). Assumptions of these analyses will be checked.

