**The main experiment:** Eligible participants will be invited to participate in the main experiment through the Prolific site. Once they sign up for the main experiment, they will be redirected to the online experiment built in Qualtrics survey platform. Participants will be first asked to sign the consent form and provided details about the study purpose and procedure. They will be informed that they will need to turn on their cameras when completing the eye-tracking task. Although their faces and surroundings will be recorded during the remote eye-tracking task, the researchers will not have access to these recordings. Consented participants will first answer several questions designed to measure baseline tobacco and alcohol consumption, alcohol-related knowledge, and the device they are currently using to be directed to the corresponding mobile or desktop-based eye-tracking experiment. Next, participants will engage with a webcam-based eye-tracking task. They will first read instructions and tips related to completing the eye-tracking task. They will then go through a calibration procedure to ensure good tracking. Participants will then be randomly assigned to view an order-randomized stimulus set containing either three narrative PWLs or three non-narrative PWLs. Narrative PWLs will contain photos of cancer

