## 7.1. Data Collection/Instruments

The screening survey questionnaire, the main experiment questionnaire, the follow-up survey questionnaire, and the experimental stimuli (i.e., narrative and non-narrative PWLs) are included in the submission. Below, we briefly describe each questionnaire.

**The screening survey:** The screening survey will include five questions related to their age, average weekly alcohol consumption, and technical support to complete eye tracking tasks.

**The main experiment:** *Pre-test measures* will assess baseline tobacco and alcohol consumption and other alcohol-related background information. Baseline tobacco and alcohol consumption are included because the combination of tobacco and alcohol significantly increase the risk for developing cancers in mouth, esophagus, and larynx, the three cancer types shown in the experimental stimuli. Other *alcohol-related background information* will be included because they may influence how participants respond to the experimental stimuli. *Post-test measures* will assess visual attention measured via the eye-tracker and a self-report question, avoidance, narrative construction, and reactance in

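### Alcohol-related knowledge and tobacco use are measured before assignment but have no role in the H1 or H2 models; prespecified, unconditional adjustment would gain a little precision at almost no cost.

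*Combined protocol and SAP*

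**What the plan says.** Section 5 (Analytical Plan) tests for "differences in background variables (i.e., demographic characteristics and baseline alcohol consumption) between conditions". The abbreviation i.e. makes this a closed list. Its rule is: "If there are a significant association between the experimental condition and a specific background variable(s), we will control for this variable(s) in all analyses". For H2, the independent-samples t-test applies "when there are no differences in the distribution of background variables between conditions", and ANCOVA replaces it only if differences are found.

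Section 7 (The main experiment) has consenting participants first answer "several questions designed to measure baseline tobacco and alcohol consumption, alcohol-related knowledge, and the device they are currently using". Calibration and then random assignment follow. Socio-demographic items come at the end of the experiment, after the labels have been seen.

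Section 7.1 gives separate reasons for the pre-test items. For tobacco and alcohol use it says: "Baseline tobacco and alcohol consumption are included because the combination of tobacco and alcohol significantly increase the risk for developing cancers". Of the other alcohol-related background items it says that they "will be included because they may influence how participants respond to the experimental stimuli". It lists risk perceptions and intentions among the post-test and follow-up measures and describes no pre-test of either.

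**The concern.** The protocol gives a reason to expect some pre-test items to predict response to the labels, and then gives those items no role in the primary analyses. Because they precede assignment, the labels cannot affect them, which makes them cleaner covariates than demographics asked after exposure. With no pre-test of risk perceptions or intentions described, the H2 models have no baseline version of the outcome to adjust for, so other pre-exposure measures are the available means of reducing residual variance.

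What is at stake is precision. Any outcome variance that these measures explain stays in the error term of the H1 and H2 comparisons.

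**Working it through.** **Inputs.** Section 6.2.1 gives alpha .05, d = .20, 80% power and N = 800 for an independent t-test. A two-sided test and 1:1 allocation are assumed, as neither is stated. R² is the share of within-condition outcome variance explained by the covariates. The documents do not give it, so a range is used.

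**1. Reproduce the planned N.** Total N = 4(1.960 + 0.842)²/0.20² ≈ 785, or 786 with equal whole arms. The noncentral t gives 788. The stated 800 is within 3% and assumes no covariates. At N = 800, unadjusted power is about 80.6%.

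**2. Power with unconditional adjustment.** Adjustment multiplies the standard error by √(1 − R²). The noncentrality becomes 0.20 × √(800/4)/√(1 − R²) = 2.828/√(1 − R²). The equivalent unadjusted sample is 800/(1 − R²).

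| Assumed R² | SE multiplier | Noncentrality | Power (t-test) | Equivalent N |
|---|---|---|---|---|
| 0 | 1.000 | 2.828 | 80.6% | 800 |
| .02 | 0.990 | 2.857 | 81.4% | 816 |
| .05 | 0.975 | 2.902 | 82.6% | 842 |
| .10 | 0.949 | 2.981 | 84.6% | 889 |

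The gains are about 0.8, 2 and 4 points.

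**3. Would it be enough to add the two measures to the balance-test list?** If condition is randomised, each is flagged with probability .05. With independent tests, the chance that either is flagged is 1 − 0.95² = 9.75%, so in roughly nine trials out of ten nothing would change. A simulation with two equally prognostic covariates (N = 800, d = .20, 4,000 replicates per setting, Monte Carlo standard error about √(0.8 × 0.2/4000) = 0.6 points) gave this power:

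| R² | Never adjust | Adjust if flagged | Always adjust |
|---|---|---|---|
| .05 | 79.9% | 80.2% | 81.9% |
| .10 | 80.4% | 80.4% | 84.0% |
| .20 | 79.8% | 80.9% | 88.6% |

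The significance-triggered rule recovers at most about 1 point. The gain comes from adjusting regardless of balance.

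**4. Skipped items.** Section 6.6 lets participants skip any part of the study. If a share m lacks a covariate and is deleted listwise, the effective sample relative to no adjustment is (1 − m)/(1 − R²). This equals 1 when m = R²: 2% missing cancels the gain at R² = .02, and 5% cancels it at R² = .05.

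**5. H1.** A person-level covariate in the mixed models can reduce between-person variance only. The documents give no variance components and no link between these measures and the eye-tracking outcomes or reactance, so no figure can be given.

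**The case against.** The strongest reply is that the closed list is not the main cause of the loss. Section 5 has no fixed covariate set. Even demographics and baseline alcohol consumption stay out of the models unless a balance test is significant. That stands, and step 3 confirms it, so the remedy has to replace the conditional rule as well as extend the list.

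Four further limits also stand:

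- The reason about influencing responses is given for the other alcohol-related background items. A reader might infer that it covers tobacco too, but tobacco's stated reason is joint cancer risk with alcohol. Treating knowledge as one of the background items is itself a reading across sections 7 and 7.1, though a natural one.
- The questionnaire is not in the text, so how closely knowledge relates to risk perceptions is unknown. Every R² above is assumed.
- Nothing in the documents shows that either measure predicts visual attention or reactance.
- Complete covariate data cannot be taken for granted, since items may be skipped.

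A reader might also infer that the planned tests are biased, or that the trial needs adjustment to reach 80% power. The documents support neither. Randomisation makes the unadjusted comparison valid, and N = 800 gives about 80.6% without covariates. None of this removes the case for using the data; it limits what can be claimed for it.

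**Conclusion.** The point holds as an efficiency improvement, not as an error in the plan. Section 5 gives alcohol-related knowledge and tobacco use no role in H1 or H2, and it uses baseline alcohol consumption only after a significant balance test. Unconditional adjustment would add about 0.8, 2 or 4 points of H2 power at N = 800 and d = .20 under assumed R² of .02, .05 or .10, given a two-sided test, 1:1 allocation and no loss of participants to missing covariates. The case is stronger for knowledge than for tobacco. For H1, the mixed models could gain in the same direction, but the size is unknown.

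**What to change.** In section 5, before any outcome is compared by condition (404 participants had already completed the main experiment, per section 6.2.1):

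- Name alcohol-related knowledge, baseline alcohol consumption and tobacco use, with their scoring, as covariates in the H2 ANCOVA and the H1 mixed models, whatever the balance tests show. This replaces the significance-triggered rule for these measures.
- Keep participants with skipped covariate items by simple imputation or a missing indicator, and rule out listwise deletion on covariates.
- Report the unadjusted result beside the adjusted one, and say in advance that the adjusted estimate is primary.

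The cost is SAP wording and a few degrees of freedom out of about 800. No new data collection is needed. If the covariates turn out to be weakly prognostic, little is gained.

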#### 6.2.1. Sample Size

No previously published work has examined the effect of narrative (vs. non-narrative) PWLs on visual attention and reactance. In our preliminary work, we conducted an online experiment testing the effect of PWLs type among adult moderate and heavy drinkers. We found that participants who saw non-narrative PWLs reported significantly higher reactance to the warnings than those who saw narrative PWLs ( $r = .19$ ).

Therefore, in the proposed project, we will use the effect size of  $r = .19$  to estimate the sample size. With the alpha level set at .05, we will need 213 participants to achieve a statistical power of .80. The final sample size needs to account for possible failure to (1) complete the eye-tracking task and (2) generate usable eye-tracking data for those who complete the task. Based on a recent remote eye-tracking study (Chen-Sankey et al., 2023) and information provided by the Sticky by Tobii team, we plan to screen 1,200 participants (41% rate of completion) and enroll 500 participants (43% rate of usable data).

Because risk perceptions and behavior intentions are also our primary outcomes, we conducted an additional power analysis to calculate the sample size for these two

outcomes. Based on previous research (e.g., Oschatz & Marker, 2020), narratives had a small effect on persuasion. With the alpha level set at .05, we would need at least 800 participants to detect an effect of  $d = .20$  with 80% power in an independent t-test.

Given that the sample size to detect a significant effect on risk perceptions and behavior intentions ( $N=800$ ) is larger than that on reactance ( $N=500$ ), we decided to enroll 800 participants in our main experiment. Accordingly, we would need to screen 1,951 participants (41% rate of completion).

Running the study resulted in 1,045 eligible participants from 1,922 screened participants. Of the 1,045 eligible participants, only 404 participants so far completed the main experiment successfully. Increasing the screener eligibility to 3,000 is expected to increase the successful completion of the main study to the projected 800.

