## 7. Study Procedures

Given that this project consists of three parts: the screening survey, the main experiment, and the follow-up survey; below is a description of each part. No personally identifying information will be collected throughout the entire project. Only participants' Prolific IDs will be used to connect data across the three parts.

**The screening survey:** Potential participants from the Prolific will first be invited to participate in a short online screening survey. The screener will be built using the Qualtrics survey platform. We will prescreen the sample to some extent using the Prolific' existing prescreening options, including currently residing in the U.S., being at least 21 years old, drinking at least one unit of alcohol on average per week, and having webcam or built-in camera that they are willing to use as part of a study. The screening survey will include five questions related to their age, average weekly alcohol consumption, and technical support to complete eye tracking tasks. Participants must meet the following inclusion criterion to be invited to participate in the main experiment: 1) be at least 21 years old; (2) have consumed more than three alcoholic drinks per week over the past year; and (3) be willing to participate in remote eye tracking tasks and have necessary technical support and physical environment to complete remote eye tracking tasks. The entire duration of the screening survey is expected to be about 1 minute.

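### Letting balance tests choose the covariates gives up a small gain in H2 precision; a fixed list, with a sensitivity model for dropout imbalance, would recover it

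*Combined protocol and SAP*

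**What the plan says.** Section 5 compares "background variables (i.e., demographic characteristics and baseline alcohol consumption) between conditions" using t-tests and chi-square tests. It continues: "If there are a significant association between the experimental condition and a specific background variable(s), we will control for this variable(s) in all analyses". For H2, the independent-samples t-test applies "when there are no differences in the distribution of background variables between conditions"; otherwise ANCOVA is used. No significance level is given for the balance tests, and no covariate is named for adjustment whatever the balance.

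Section 7.1 lists ten socio-demographic items. Section 7 places them at the end of the main experiment, after the labels have been shown. Baseline alcohol and tobacco use, alcohol-related knowledge and device type are recorded before exposure. Of these four, Section 5 lists only baseline alcohol among the screened variables. Section 7.1 justifies collecting the other alcohol-related background items on the ground that they may affect how participants respond to the labels.

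On size, Section 6.2.1 says "we would need at least 800 participants to detect an effect of" d = .20 with 80% power in a t-test at alpha .05.

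**The concern.** Under random assignment, a balance p-value reflects chance. It carries no information on whether a variable predicts risk perceptions or intentions, and prediction is what makes adjustment useful. A rule that selects on balance will usually leave out a strongly prognostic variable and will sometimes admit a useless one. Two things are at stake. The first is precision available from data already collected. The second is that the primary H2 model cannot be named before the data are seen: the procedure is written in advance, but the covariate set is not.

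**Working it through.** **Inputs.** From Section 6.2.1: N = 800, d = .20, alpha .05, 80% power, r = .19 for reactance, and 43% usable eye-tracking data. From Section 7.1: ten socio-demographic items, which with baseline alcohol make 11 screened variables. Assumed: 1:1 allocation, two-sided tests, balance tests at .05, and R² of .03, .05 or .10.

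**1. The plan's own figure.** An exact two-sided t-test for d = .20 at 80% power needs 394 per arm, 788 in total. At 400 per arm the power is .8065. The stated 800 is reproduced.

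**2. How often adjustment is triggered.** For k independent tests the chance is 1 − .95^k:
- k = 7: .302
- k = 8: .337
- k = 11: .431

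With 11 tests correlated at .3 it is about 37–38%. In simulation each screened variable entered in .049 to .051 of trials. A separate run with R² from 0 to .50 gave 4.7% to 5.5%, with no relation to prognostic strength.

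**3. H2 power under three approaches.** There were 10,000 simulated trials per setting, with N = 800, d = .20 and randomisation intact. Eleven variables were screened (alcohol, age, sex and eight others); tobacco and knowledge were not. The fixed list is alcohol, age, sex, tobacco and knowledge. Cells show t-test / current rule / fixed list.

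| Where the R² lies | R² .03 | R² .05 | R² .10 |
|---|---|---|---|
| All on list, independent | .806/.807/.815 | .805/.806/.824 | .807/.807/.842 |
| All on list, correlation .3 | .809/.814/.821 | .806/.811/.826 | .808/.813/.846 |
| Half on list, independent | .809/.810/.814 | .807/.808/.813 | .814/.813/.828 |
| Half on list, correlation .3 | .808/.805/.812 | .806/.812/.823 | .810/.819/.840 |

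The gain of the fixed list over the rule runs from 0.4 to 3.5 points. The Monte Carlo standard error is about 0.4 points per power. The rule stays within 1 point of the t-test throughout. Its null rejection rate was .048 to .052.

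**4. Analytic ceiling.** Replacing d by d/√(1 − R²) gives power of .818, .826 and .846 at R² .03, .05 and .10. The most that can be gained over the t-test is .846 − .807 = 3.9 points. In completers, 800/(1 − R²) − 800 gives 12 at R² .015, 42 at .05 and 89 at .10.

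**5. H1.** For reactance, d = 2(.19)/√(1 − .19²) = .387. With .43 × 800 = 344 usable participants a simple t-test has power .947; with 800 it has .9998. No material gain is claimed. The documents give no effect size for attention.

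**6. If dropout breaks the balance.** Suppose dropout leaves an unlisted covariate imbalanced by s standard deviations, with no true effect. A model omitting it is shifted by z = s√R²/√(4/800), and rejects with probability P(|Z + z| > 1.96):
- s = .2, R² .05: z = .2 × .2236/.0707 = .63, rejection about 10%.
- s = .2, R² .10: z = .2 × .3162/.0707 = .89, rejection about 14%.
- s = .1, R² .05 and .10: about 6% and 7%.

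The current rule rejects about 5% in these settings, because the imbalanced variable often enters: about 80% of the time at .2 SD and 28–29% at .1 SD. A model with the fixed list plus any screened variable found imbalanced also rejects about 5%, and it keeps the power gain of step 3.

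**The case against.** The strongest counter-argument is that the existing rule protects against something a fixed list alone does not. In Section 7, assignment follows calibration. Under Section 6.9, anyone terminated by the eye-tracking platform, including by closing the browser, has their data removed. One arm sees diseased organs and the other sees patients, so losses after assignment could differ by arm. The 5% entry rate would then no longer hold, and step 6 shows that a fixed list omitting an imbalanced prognostic variable could do worse than the current rule. This stands and shapes the fix. It remains a possibility: the documents give no post-assignment dropout rate, and calibration failures precede assignment.

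It is also fair to say that the rule is a pre-specified algorithm, that the gain rests on assumed R², and that age and sex are conventional choices not shown here to be prognostic.

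A reader might infer that the rule inflates type I error or leaves H2 underpowered. Neither follows: null rejection is about .05 and power is about .80. Nor do the documents show that tobacco, knowledge or device can never be adjusted for. They are not listed among the screened variables, but the drafting is loose and Section 7.1 uses background information in a wider sense.

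**Conclusion.** The point holds as a small, optional-level improvement in efficiency and clarity. With randomisation intact and balance tests at .05, the rule performs like the unadjusted t-test, and always adjusting would add about 0.4 to 3.5 points of H2 power for R² up to .10. The lower part of that range is the more plausible, because the documents list no pre-exposure measure of risk perceptions or intentions. The change is nearly free only if a safeguard against differential dropout is kept. The entry rate is well established under its assumptions; the size of the gain depends on an R² that the documents do not supply.

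**What to change.** Make a dated change before outcome analysis:

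- Make the primary H2 analysis an ANCOVA that always adjusts for a short named list of pre-exposure or stable variables: baseline alcohol, baseline tobacco, alcohol-related knowledge if the questionnaire yields a usable score, age and sex.
- Do not use balance tests to choose primary covariates. Because the present trigger covers every analysis, state what replaces it in the H1 models; the same list would be consistent, though no H1 power gain is claimed.
- Keep the unadjusted t-test as a sensitivity analysis.
- Pre-specify a second sensitivity model that adds to the fixed list any screened background variable found imbalanced, and state the criterion for imbalance.
- Report terminations by arm, if the platform provides them.

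On timing of measurement, Section 7 says "The screening survey will include five questions related to their age, average weekly alcohol consumption, and technical support to complete eye tracking tasks", so a pre-exposure age may be linkable by Prolific ID. Sex is asked after the labels but is stable. The questionnaires are not part of the document, so the form of the age and knowledge items must be checked.

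The cost is a slightly larger model, one extra sensitivity analysis, and a plan change made when, per Section 6.2.1, "only 404 participants so far completed the main experiment successfully". No new data are needed.
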